14.2.8 Duration of Response (Secondary Endpoint)

Duration of Response (DOR) is defined for participants with a confirmed objective response as the time from first documentation of a confirmed objective response (CR or PR) according to RECIST 1.1 to the date of first documentation of objective progression of disease (PD) or death due to any cause, whichever occurs first. The censoring rules for DOR are as described for PFS (Table 7).

DOR = (date of PD or death or censoring – date of confirmed objective response + 1)/30.4375 (months).

DOR of confirmed CR/PR according to RECIST 1.1 as measured by the IRC and the Investigator will be described. Considering confirmed CR/PR involve having at least two objective responses, the date of occurrence of the first CR/PR will be used as date of objective response.

Frequency (number and percentage) of participants with an event, with ongoing response at data cut-off date and without event will be presented as well as the DOR time Med, Min, and Max. Number of participants at risk, failed and DOR rates with their CI at 3, 6, 9, 12, 18 and 24 months will also be provided.

The analysis of DOR will be performed with a Kaplan-Meier method (product-limit estimates) and a summary of associated statistics will be presented including corresponding two-sided 95% CIs. The CIs for the Med will be calculated according to Brookmeyer and Crowley (1982) and CIs for the survival function estimates will be derived using the log-log transformation according to Kalbfleisch and Prentice (1980) (CONFTYPE = loglog default option in SAS PROC LIFETEST). The estimate of standard error will be computed using Greenwood's formula.

DOR rates with their CI at 3, 6, 9, 12, 18 and 24 months will be presented, as well as the number of participants at risk and failed.

The time to and duration of response per participant having a confirmed objective response (including delayed response, see section 14.2.12 below) will be displayed in swimmer graphs. Kaplan-Meier figures will also be provided.

Listings will be provided with the following information: participant identifier, age, sex, race, date of first study treatment administration, date of first response, date of last tumor assessment, censored (Y/N), date of event/censoring, event/censoring reason, duration of response and if the response is ongoing (administrative censoring for subject ongoing in the study without an event).

CCI

14.2.10 Durable Response Rate (Secondary Endpoint)

Durable Response Rate (DRR) is defined as the number of participants having a DOR of at least 6 months, out of the total number of participants. Participants for whom the DOR is censored will be treated as failures (successes) in the analysis of durable response if the censored DOR is below (at least) 6 and 12 months.

The DRR will be provided with a two-sided 95% CI using the Clopper-Pearson method (exact CI for a binomial proportion as computed by default by the FREQ procedure using the EXACT option).

DRR of at least 12 months will also be provided.

DRR will be described according to RECIST 1.1 as measured by the IRC and the Investigator.

CCI

14.2.13 Overall Survival (Secondary Endpoint)

Overall survival (OS) is defined as the time from first administration of study treatment to the date of death due to any cause:

OS = (date of event or censoring – date of the first dose + 1)/30.4375 (months).

For participants alive at the time of data cut-off date or who are lost to follow up, OS will be censored at the last date known to be alive. The date of event / censoring is defined in Table 8.

Table 8 Survival Event / Censoring

Survival Status	Date of event/censoring	Censoring
Participants alive or lost to follow-up before or at cut-off date	Last date known to be alive	Yes
Participants who died before or at cut-off date	Date of death	No

Last date known to be alive will be derived as specified in Section 9.6.

The analysis of OS time will be performed with a Kaplan-Meier method with the same approach as for PFS described in section 14.2.4. Kaplan-Meier estimates (product-limit estimates) will be presented together with a summary of associated statistics including corresponding two-sided 95% CIs. OS rates with their CI at 3, 6, 9, 12, 18 and 24 months will be presented, as well as the number of participants at risk and failed. Censoring reasons will also be described. Censoring reasons are as follows:

- Alive at cut-off date
- Withdrawal of consent
- Lost to follow-up

OS will also be presented graphically with Kaplan-Meier figures.

A participant listing will provide the following information: participant identifier, age, sex, race, date of first study intervention, date of event/censoring, event/censoring reason, time to event.

CCI

CCI

15 Safety Analyses

Analysis set: SAF

The subsections in this section include specifications for summarizing safety endpoints that are common across clinical studies such as adverse events, laboratory tests and vital signs.

Additional analyses may be performed on safety events to explore specific risk factors.

15.1 Adverse Events

Treatment-emergent adverse events (TEAEs) are those events with onset dates occurring during the on-treatment period or if the worsening of an event is during the on-treatment period.

Changes in toxicity grade, seriousness or outcome of AEs are recorded as separate entries in the eCRF. Such entries reporting the same event in such immediately consecutive periods will be considered as one event in the analysis (using the field “AE id for new grade” in the eCRF). These events will be kept as separate records in the database in order to maintain the full detailed history of the events. The start date of the initial record in the sequence is taken as start date of the entire event, similarly the end date of the last event in the sequence is taken as end date of the entire event. The overall outcome of the adverse event is the outcome of the last event in the sequence. Duration of the AE and the TEAE flag will be adjusted accordingly in the analysis.

All analyses described in this section will be based on TEAEs if not otherwise specified. The AE listings will include all AEs. AEs during on-treatment period will be flagged in listings. AE occurring during the reinitiation phase will be considered as TEAE and will be reported in the summary tables and will be flagged in the listings.

Incomplete AE-related dates will be handled as stated in Section 9.9.

Related Adverse Events are those events with relationship to study treatment (as recorded on the “Adverse Events Details” eCRF page, Relationship with Bintrafusp alfa= Related) reported by the Investigator and those of missing or unknown relationship.

Serious Adverse Events (SAE) are those events reported on the “Adverse Events Details” eCRF page, with the “Serious Adverse Event” field ticked “Yes”.

Adverse Events Leading to Temporary Discontinuation are those events leading to temporary discontinuation of study treatment (answer to the question “Action(s) taken with Bintrafusp alfa” = “Drug interrupted” on “Adverse Event Details” eCRF page).

Adverse Events leading to Permanent Treatment Discontinuation are those events leading to permanent discontinuation of study treatment (answer to the question “Action(s) taken with Bintrafusp alfa” = “Drug withdrawn” on “Adverse Event Details” eCRF page).

Adverse Events leading to Death are those events leading to death (as recorded on the “Adverse Event Details” eCRF page, change in grade = “No” and outcome = “Fatal”, or Grade = “Grade 5 or death related to AE” or Serious adverse event = “Yes” and seriousness criteria include “Results in death”).

Adverse Events of Special Interest (AESI): AESI are identified according to a pre-specified search list of MedDRA Preferred Terms (PTs) which will be finalized before the database lock. Categories of AESI include:

- Infusion-Related Reactions (IRRs)
- 
- TGF-β inhibition mediated Skin Reaction Anemia
- Bleeding events

The tables in this section may be repeated for China sub-population.

15.1.1 All Adverse Events

Adverse events will be summarized by worst severity (according to National Cancer Institute - Common Terminology Criteria for Adverse Events [NCI-CTCAE] version 5.0) per participant, using the latest available version of MedDRA PT at the time of the database lock as event category and MedDRA primary SOC body term as Body System category.

Unless otherwise stated adverse events will be displayed in terms of frequency tables: PTs and primary SOCs in alphabetical order.

Each participant will be counted only once within each PT or SOC. If a participant experiences more than one AE within a PT or SOC for the same recording period, only the AE with the strongest relationship or the worst severity, as appropriate, will be included in the summaries of relationship and severity.

If an adverse event is reported for a given participant more than once during treatment, the worst severity and the worst relationship to study treatment will be tabulated. In case a participant had events with missing and non-missing grades, the maximum of the non-missing grades will be displayed.

A table presenting the overall summary of AEs will be presented including the frequency (number and percentage) of participants within each of the following categories:

- TEAEs
- Related TEAEs
- Serious TEAEs
- Related Serious TEAEs
- TEAEs NCI-CTCAE severity grade (≥ 3 , ≥ 4)
- Related TEAEs NCI-CTCAE severity grade (≥ 3 , ≥ 4)
- TEAEs leading to death
- Related TEAEs leading to death
- AEs of special interest:
 - Infusion-related reactions (IRRs)
 - CCI [REDACTED]
 - TGF- β inhibition mediated skin adverse events
 - Anemia
 - Bleeding events
- Related AEs of special interest:
 - Infusion-related reactions (IRRs)

- TGF- β - inhibition mediated skin adverse events
- Anemia
- Bleeding events

Tables for TEAEs frequency corresponding to each category in the overview table above will be provided by:

- MedDRA primary SOC (ordered alphabetically) and PT (ordered alphabetically), (except for AE of special interest and TEAE with NCI-CTCAE severity grade ≥ 3 or ≥ 4).

TEAEs and related TEAEs by worst grade will also be summarized, and the most frequent PTs (at least 5%) will be presented graphically by worst grade and PT with bar chart figures.

Clinicaltrials.gov and EudraCT - requirements

Summary table for non-serious TEAEs excluding SAEs applying frequency threshold of 5% will be provided.

Listings of adverse events will contain the following information: participant identifier, age, sex, race, first and last date of study intervention, PT, reported term for the AE, start date, end date, duration of AE (in days), day relative to the first infusion, day relative to the most recent infusion prior to AE onset, relationship to study treatment, toxicity grade, action(s) taken, outcome, seriousness (Y/N), AESI infusion-related (Y/N), AESI immune-related (Y/N), TGF- β inhibition mediated skin adverse events (Y/N), bleeding (Y/N), anemia AESI (Y/N), AE occurring after COVID-19 pandemic start (Y/N). TEAEs and AEs occurring during the reinitiation period specifically will be flagged.

Following listings will be provided with the relevant information:

- Listing of all AEs (whether treatment-emergent or not) (TEAEs will be flagged) (AEs occurring during reinitiation phase will be flagged)
- Listing of TEAEs
- Listing of non-TEAEs for AEs starting and not worsening after enrollment (date of first signature of informed consent/date of first signature of first informed consent) but prior to the first dose of study intervention.
- Listing of AEs with onset or worsening after the on-treatment period (AEs occurring during reinitiation phase will be flagged)
- Listing of all AEs for reinitiated participants

Evaluation of Potential Effect of ADA and nAb on Bintrafusp alfa Safety

The following analyses frequency and percentage of AEs by ADA status (ever positive, never positive), and by nAb status (ever positive for either assay, never positive) will be performed:

- TEAEs
- TEAEs, grade ≥ 3
- TEAEs leading to permanent treatment discontinuation

- TEAEs excluding IRRs leading to drug interruptions
- Serious TEAEs
- TEAEs leading to death
- irAEs (see definition in Section 15.2.3.2)
- IRRs (see definition in Section 15.2.3.1)

Listings of all AEs and all IRRs for ever-positive ADA participants (pre-existing, transient treatment-emergent, persistent-treatment emergent) will be prepared including participant identifier and showing the date(s) of the positive ADA result together with the AEs or IRRs. For the AEs and IRRs, start and stop date will be shown along with grade. Adverse events recorded during the period of 2-weeks prior to the positive ADA value till two weeks after the positive ADA value will be flagged. This will be repeated for ever-positive nAb participants in either assay (PD-L1 and TGF- β).

Evaluation of COVID-19 effects on AEs

The direct effect of COVID-19 for AEs will be assessed via listing of COVID-19 related AEs. The following listing will be generated using the ‘COVID-19 related terms using the latest available version of MedDRA update Spreadsheet’ (<https://www.meddra.org/covid-19-related-terms-meddra-230-update-spreadsheet>, last accessed on 28 May 2020) as available from Maintenance and Support Services Organization (MSSO), considering all ‘search terms for COVID-19-related’ =’Y’. Same information as for the listing of all AEs will be provided.

15.1.2 Adverse Events Leading to Discontinuation of Study Treatment

Frequency tables summarizing the following actions taken with study treatment will be presented by PT and primary SOC in alphabetical order:

- TEAEs leading to temporary treatment interruption
- Related TEAEs leading to temporary treatment interruption
- TEAEs leading to permanent treatment discontinuation
- Related TEAEs leading to permanent treatment discontinuation
- TEAEs leading to infusion rate reduction
- Related TEAEs leading to infusion rate reduction

In addition, the incidences for above items will be summarized in an overview table.

The listing of TEAEs leading to permanent treatment discontinuation will also be provided with the relevant information.

15.2 Deaths, Other Serious Adverse Events, and Other Significant Adverse Events

15.2.1 Deaths

All deaths, deaths within 30 days after last dose of study treatment (in case of reinitiated participants, the last dose will be the last dose of the reinitiation phase), death within 60 days after first dose of study treatment (for all participants, the first dose will be the first dose of the first treatment phase) as well as the primary reason for death will be tabulated based on information from the “Death” eCRF pages.

The following summaries will be provided:

- Number of deaths (including deaths during reinitiation phase)
- Number of deaths within 30 days after last dose of study treatment
- Number of deaths within 60 days after first dose of study treatment
- Primary Reason for Death
 - Progressive disease and/or disease related condition
 - Event unrelated to study treatment
 - Event related to study treatment
 - Unknown

In addition, date and cause of death will be provided in an individual participant data listing together with following dosing information: participant identifier, age, sex, race, date of first/last study intervention, number of infusions, day relative to the first and the last infusion, primary reason, autopsy (Y/N/U), AEs with fatal outcome (list PTs of AEs with outcome = Fatal, as well as Grade 5 or Serious resulting in death), flag for death within 30 days of last dose of study treatment and flag for death within 60 days of first dose of study treatment.

The tables and listings in this section may be repeated for China sub-population.

15.2.2 Serious Adverse Events

The following overall frequency tables will be prepared for serious adverse events (SAEs):

- Incidence of serious AEs by SOC and PT
- Incidence of related serious AEs by SOC and PT

The listings of SAEs will also be provided with the relevant information with a flag for TEAEs and AEs occurring during reinitiation phase (see description of listing in Section 15.1.1).

This may be repeated for China sub-population.

15.2.3 Adverse Events of Special Interest

The tables in this section may be repeated for China sub-population.

15.2.3.1 Infusion-Related Reaction including Immediate Hypersensitivity

Infusion-Related Reactions (IRRs) are defined as adverse events with PTs according to a pre-specified MedDRA search list which will be finalized before database lock, and are divided into two subcategories: “Reactions” and “signs and symptoms” based on criteria on the timely relationship as detailed below:

Reactions of IRR: will be considered when onset is on the day of infusion (during or after the infusion) or the day after the infusion (irrespective of resolution date) for any infusion-related reaction, drug hypersensitivity, anaphylactic reaction, hypersensitivity and/or Type 1 hypersensitivity.

Signs and symptoms of IRRs and hypersensitivity/allergic reactions: will be considered when onset is on the day of infusion (during or after the infusion) and resolved completely with the end date on the same day of the infusion or the day after for any of the following: pyrexia, chills, flushing, hypotension, dyspnea, wheezing, back pain, abdominal pain and urticaria.

IRR, overall and by subcategories, will be summarized by the following variables:

- Number of participants with at least one IRR by the worst NCI-CTCAE toxicity grade (grade 1/ grade 2/ grade 3/ grade 4/ grade 5/ missing grade)
- Number of participants with IRR leading to permanent treatment discontinuation.
- Time related to first onset (infusion 1/ infusion 2/ infusion 3/ infusion 4 or later). The events will be assigned to the actual drug infusions that the participant received, not to the planned dates. An IRR is assigned to a drug infusion if its onset is at the same date and time is missing or same or after dosing (but not before dosing when time is recorded) or the following day of drug infusion.

The frequency table of IRR and drug related IRR AEs by worst grade, SOC, and PT will also be provided.

The listing of IRRs will be provided with the relevant information (see description of listing in Section 15.1.1). One additional listing will display the study drug administration details together with the infusion-related adverse event including administration date (day) /time, reason for modification, type of modification, modification start time, use of pre-medication, IRR AE Preferred Term, IRR AE grade, IRR AE start day /stop day, IRR AE time related to infusion.

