6.9.1 Infusion-related Reactions Including Immediate Hypersensitivity

Infusion-related reactions including immediate hypersensitivity, are defined in this section. Infusion-related reactions are AESIs and identified risks for bintrafusp alfa.

Infusion-related Reactions

Infusion-related reactions are defined as any signs or symptoms experienced by participants during the infusion of pharmacologic or biologic agents or any event occurring during or within 1 day of study intervention administration. They are identified based on a list of Medical Dictionary for Regulatory Activities (MedDRA) preferred terms and criteria on the timely relationship to an infusion. Events are divided into reactions versus signs and symptoms:

- Reactions are considered when onset is on the day of infusion (during or after the infusion) or the day after the infusion (irrespective of resolution date) for IRR, drug hypersensitivity, anaphylactic reaction, hypersensitivity, and type 1 hypersensitivity.
- Signs and symptoms of IRR and hypersensitivity/allergic reactions are considered when onset is on the day of infusion (during or after the infusion) and resolved completely with the end date within 2 days after onset of (but not limited to) pyrexia, chills, flushing, hypotension, dyspnea, wheezing, back pain, abdominal pain, and urticaria.

Management of Infusion-related Reactions

Premedication prior to bintrafusp alfa administration for the first 2 infusions is optional and at the discretion of the Investigator. If an Investigator chooses to administer premedications, premedication with an antihistamine and with paracetamol (acetaminophen) (e.g., 25 to 50 mg diphenhydramine and 500 to 650 mg paracetamol [acetaminophen] IV or oral equivalent) approximately 30 to 60 minutes prior to each dose of bintrafusp alfa is recommended.

If Grade ≥ 2 infusion reaction(s) are seen during the first 2 infusions, premedication should be continued/implemented for future infusions.

An assessment for possible IRR should be triggered based upon the development of specific symptoms within 24 hours of an infusion.

Management of symptoms should follow the guidelines shown in **Error! Reference source not found.**

Table 5 Treatment Modification of Bintrafusp alfa for Symptoms of Infusion-related Reactions Including Immediate Hypersensitivity

NCI-CTCAE v5.0 Grade	Treatment Modification

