3.0	1July2021	PPD	
 - Update in section 7.1: 
 - listing of COVID-19 impact added - COVID-19 vaccination related outputs added - [Redacted] CCI - Update in section 8.2: 
 - describe analyses for China and Japan authorities - Number of prior treatment lines, Prior anti-cancer RT and HPV status by central lab definition updated for clarification - ADA treatment-emergent status added - Section 9.1 Data Handling After Cut-off Date - [Redacted] CCI - Section 9.9 added some clarifications on Rules to define previous and/or concomitant medication table - Updated section 9.11 Moore criteria - Updated section 10.2.1: Important Protocol Deviations reporting - Section 11.3.2: added clarification for HPV calculation - Updated section 12.4 Previous anticancer treatments and procedures including CCRT description - Updated section 13 Cumulative dose and relative dose intensity formulas - Section 14 Non-CR/Non-PD options added for BOR calculations - Section 14.1.1 waterfall with subgroups added - Updated section 14.2.4 censoring reasons categories - Section 15.4 removed "except oxygen saturation" - Updated section 16.3 - [Redacted] CCI - Longitudinal analysis of change from baseline - Updated Section 16.4 Immunogenicity analyses - [Redacted] CCI
4.0	21February2022	PPD	
 - Section 6: Added "Overview of Planned Analyses after discontinuation of NSCLC and BTC trials"

4 Purpose of the Integrated Analysis Plan

The purpose of this integrated analysis plan (IAP) is to document technical and detailed specifications for interim, primary and final analyses of data collected for protocol MS200647_0017.

Results of the analyses described in this IAP will be included in the Clinical Study Report (CSR). Additionally, the planned analyses identified in this IAP may be included in regulatory submissions or future manuscripts. Any post-hoc, or unplanned analyses performed to provide results for inclusion in the CSR but not identified in this prospective IAP will be clearly identified in the CSR.

The IAP is based upon Section 9 (Statistical Considerations) of the study protocol and is prepared in compliance with International Council for Harmonization (ICH) Guideline E9. It describes analyses planned in the protocol.

5 Objectives and Endpoints

Table 1 Study Objectives and Endpoints

Objectives	Endpoints (Outcome Measures)	IAP section
Primary		

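### The SAP's end-date window for infusion-related signs and symptoms is one day shorter than the protocol's, so the IRR tables may undercount and cannot overcount on this criterion

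*SAP*

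**What the plan says.** Both documents split IRRs into reactions and signs and symptoms.

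For signs and symptoms, protocol 6.9.1 sets the onset rule as "Signs and symptoms of IRR and hypersensitivity/allergic reactions are considered when onset is on the day of infusion (during or after the infusion"). The event must also have "resolved completely with the end date within 2 days after onset of (but not limited to) pyrexia, chills, flushing" and six further named symptoms.

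SAP 15.2.3.1 keeps the infusion-day onset rule and names the same nine symptoms, but requires that the event "resolved completely with the end date on the same day of the infusion or the day after".

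For reactions the documents agree. Onset may be on the infusion day "or the day after the infusion (irrespective of resolution date) for any infusion-related reaction" or one of the named hypersensitivity terms, and neither document sets a resolution limit.

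On status, the protocol says "Infusion-related reactions are AESIs and identified risks for bintrafusp alfa". AESIs belong to the secondary safety objective (protocol Table 3, SAP Table 1), and SAP 6.1 keeps them in the restricted analysis for the abbreviated CSR. SAP Section 4 says of itself: "It describes analyses planned in the protocol".

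**The concern.** The two resolution windows differ by one calendar day, and no visible SAP text says that a change was intended or gives a reason for it. The legible entries of the SAP modification history do not mention an IRR window.

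SAP 15.2.3.1 uses this definition for the number of participants with an IRR, worst grade, IRRs leading to permanent discontinuation and the infusion of first onset. A narrower rule can only take events out of those tables. Under the full plan in SAP 15.1.1 it would also affect IRRs by anti-drug-antibody status, and move the omitted events into the category of interruptions due to events other than IRRs.

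**Working it through.** No stated figure has to be reproduced. The check is to apply both rules to the same event and compare.

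**Inputs**

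- Onset: the infusion day, called D, in both documents.
- SAP end-date rule (15.2.3.1): end on D or D+1.
- Protocol end-date rule (6.9.1), plain reading: end date − onset date ≤ 2 days. With onset on D, this means an end on D, D+1 or D+2.
- Alternative protocol reading, counting the onset day as day 1: end date − onset date + 1 ≤ 2. This means an end on D or D+1.

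Because onset is fixed at D in both documents, the SAP's anchor (infusion day) and the protocol's anchor (onset) are the same day, so the windows compare directly.

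| End date | SAP | Protocol, plain reading | Protocol, onset day = day 1 |
|---|---|---|---|
| D | counts | counts | counts |
| D+1 | counts | counts | counts |
| D+2 | does not count | counts | does not count |
| D+3 or later | does not count | does not count | does not count |

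On the plain reading the rules differ only at D+2. No end date meets the SAP rule and fails the protocol rule, so any discrepancy on this criterion is downward.

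**Which reading.** The protocol's own usage favours the plain one. Its general IRR definition in 6.9.1 takes in events up to 1 day from administration, and its reactions rule spells out the infusion day or the following day. One day there reaches D+1, so two days after onset reaches D+2.

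**Scale.** A participant disappears from the IRR count only if a symptom ending on D+2 is her sole qualifying IRR. The documents give no rate for this. With the planned 135 participants and an assumed share q, the number missed is 135 × q:

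- q = 0%: 0
- q = 1%: 1.35, about 1
- q = 2%: 2.7, about 3
- q = 5%: 6.75, about 7

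As a scale check, protocol 2.3 puts the earlier rate of all treatment-related IRRs below 5%, which is fewer than 135 × 0.05 = 6.75 participants. That figure covers related events only, whereas SAP IRRs are not restricted to related events, so it is not a strict bound. It does suggest that the top of the range is generous.

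**The case against.** The strongest points on the other side are these.

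- **The difference may be only a counting convention.** SAP 9.4 calculates durations as stop − start + 1, so an event from D to D+1 lasts 2 days and the rules would agree. This is possible, but that formula defines durations and does not say how to read a limit set after onset. The protocol's usage in the same section points the other way.
- **The SAP is where such details belong.** Protocol 9.4.2 leaves analysis specifics to the analysis plan, and most of SAP Section 7 (changes to planned analyses) is redacted, so a declared change cannot be excluded. That stands. If there is one, 15.2.3.1 should refer to it.
- **The events are not lost.** They stay in the general tables of treatment-emergent, serious and discontinuation events (SAP 15.1.1, 15.1.2), and the listings carry start date, end date and day relative to the last infusion. Only the AESI label is affected. This stands and limits the consequence.
- **Serious reactions are largely protected.** Events coded as infusion-related reaction, anaphylactic reaction or a named hypersensitivity term count regardless of resolution date. Worst grade and discontinuation counts change only if the D+2 symptom is itself the participant's worst or treatment-ending IRR.

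A reader might also infer that the SAP loses events by closing an open list of symptoms. The documents do not establish that. Both identify IRRs through a list of MedDRA terms, the nine named symptoms are identical, and the SAP's search list is not shown. An open-ended list has to be fixed before it can be programmed. What remains is an ambiguity about whether the nine terms or the search list governs.

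**Conclusion.** The mismatch is real and one-directional. On the plain reading of protocol 6.9.1, signs and symptoms that start on the infusion day and end on D+2 are IRRs under the protocol and not under the SAP. The IRR tables may therefore undercount this AESI, and cannot overcount it on this criterion.

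The size is unknown. The range of 0 to about 7 of 135 participants rests on the assumption that 0% to 5% had such a symptom as their only qualifying IRR.

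Two stronger readings are not supported. A reader might assume that 5% to 10% of participants, about 7 to 14, are affected. Nothing in the documents gives that rate, and it would put this single one-day slice at or above the whole related-IRR background rate quoted in protocol 2.3. A reader might also say that the SAP removes longer-lasting symptoms in general. It does not, because the protocol itself excludes anything ending on D+3 or later.

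This is a small definitional inconsistency in a secondary safety endpoint, and it should be corrected or declared.

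**What to change.** In SAP 15.2.3.1, for the signs-and-symptoms subcategory only:

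1. Change the end-date rule to no later than onset date + 2 days, keeping onset on the infusion day.
2. Leave the reactions subcategory without a resolution limit. Applying the new limit to the whole MedDRA list would contradict protocol 6.9.1 and could lower the count.
3. State whether the nine named symptoms or the pre-specified MedDRA search list governs, consistent with the protocol's open wording.

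If the shorter window is intended, declare it as a change from the protocol and give the reason; protocol 9.4 provides the amendment or the CSR for major modifications.

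The cost is one line of text and one of programming. The start and stop dates are already collected, so no new data are needed. The reported IRR rate may be slightly higher.
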